## 2. INTRODUCTION

C3731001 (Sangamo reference: SB-525-1603) is a phase 1/2, open-label, single-dose, dose-ranging study. The dose selection and number of participants studied at each dose level will be based on safety and kinetics of circulating factor VIII (FVIII) activity levels observed in previously dosed participants.

The adaptive design of this phase 1/2 study assigns participants to PF-07055480 (Sangamo reference SB-525) dose levels based on the average of FVIII activity levels in the 2 participants of a dose level/cohort. Details are provided below.

For each cohort, the first dosed participant will be followed for 6 weeks before a second participant can be dosed. After the second participant in a cohort is followed for 6 weeks, the external Data Monitoring Committee (eDMC) will meet and recommend either a dose escalation, dose de-escalation, or cohort expansion (with potential reassessment of participant's data) based on their review of the cumulative data available from the first 2 participants of a cohort.

This statistical analysis plan (SAP) provides the detailed methodology for summary and statistical analyses of the data collected in Study C3731001. This document may modify the plans outlined in the protocol; however, any major modifications of the primary endpoint definition or its analysis will also be reflected in a protocol amendment.

Any deviations from the SAP will be described in the Clinical Study Report.

## 2.1. Study Objectives, Endpoints, and Estimands

Estimands have not been defined for this study.

Objectives	Endpoints
Primary objective	
Primary endpoints
 
 
• To evaluate the safety and tolerability of SB-525 (PF-07055480).
 

	
 
• Incidence of adverse events (AEs) and serious adverse events (SAEs) including clinically significant changes in physical examination, clinical laboratory assessments, immune parameters, vital signs, electrocardiogram (ECG), liver imaging
 
 
 
• To evaluate the time-course profile of FVIII activity after dosing with SB-525 (PF-07055480).
 

Secondary objectives	
Secondary endpoints
 
 
• To evaluate clinical impact (efficacy and quality of life) on hemophilia after dosing with SB-525 (PF-07055480).
 
 
 
• To evaluate immune response to FVIII.
 

 
To evaluate vector shedding of adeno-associated vector 2/6 (AAV 2/6).
 
	
 
Detection of adeno-associated vector 2/6 (AAV2/6) vector deoxyribonucleic acid (DNA) by polymerase chain reaction (PCR) in plasma, saliva, urine, stool and semen
 

Exploratory objectives	Exploratory endpoints

 
To evaluate the concurrence between FVIII levels by enzyme-linked immunosorbent assay (ELISA) (FVIII antigen) and by FVIII activity assays.
 
To further investigate SB-525 (PF-07055480) mechanism of action and immune responses.
 
	
 
Measurements of FVIII antigen levels
 
Measurements of neutralizing activity and antibodies to AAV2/6, as well as T-cell responses to AAV2/6 and FVIII
 
Measurements of von Willebrand Factor (vWF), C-reactive protein (CRP) and interleukin-6 (IL6)
 

Optional liver biopsy substudy only: 
 
To evaluate vector integration in the liver
 
To evaluate the histopathology of the liver tissue
 
To assess the expression of protein and/or RNA levels of FVIII and other biomarkers of interest in the liver
 
	
 
For the integrations analyses (as feasible, ie, depending on the quantity of biological material collected): the number and location of integration sites, the location of the integration sites relative to transcription start sites, the nature of the inserted sequence, the frequency of insertions, and the frequency and distribution for each size and type of insertion
 
Other exploratory endpoints (as feasible): histopathology assessment (eg, presence of fibrosis assessment, presence of lymphocytic invasion), protein and/or RNA expression of FVIII and selected biomarkers (eg, Grp78, Gal3BP)
 

## 2.2. Study Design

### Number of Participants:

Approximately 20 participants may be enrolled in this study. The dose selection and number of participants studied at each dose level will be based on safety and the cumulative kinetics of circulating FVIII levels observed in previously dosed participants.

[figure not shown]
### Intervention Groups and Duration:

The possible clinical dose level range will be from  $6 \times 10^{11}$  vector genome (vg)/kilogram (kg) to  $6 \times 10^{13}$  vg/kg, with a starting dose of  $9 \times 10^{11}$  vg/kg, which is expected to yield >5% normal FVIII levels in 57% of treated participants. Several dose levels may need to be studied to identify a safe and tolerable therapeutic range. If observed FVIII levels at the starting dose level of  $9 \times 10^{11}$  vg/kg are higher than anticipated, then dose de-escalation to  $6 \times 10^{11}$  vg/kg will be considered.

Dose levels considered include:

Possible Total Recombinant Adeno-Associated Viral Vector (rAAV) Dose (vg/kg)
$6 \times 10^{11}$
$9 \times 10^{11}$
$1.2 \times 10^{12}$
$2 \times 10^{12}$
$4 \times 10^{12}$
$6 \times 10^{12}$
$1 \times 10^{13}$
$2 \times 10^{13}$
$3 \times 10^{13}$
$4 \times 10^{13}$
$5 \times 10^{13}$
$6 \times 10^{13}$

The duration of study participation will be approximately 62 months for each participant, divided into approximately 8 weeks (2 months) for screening, and 60 months study follow-up following a single infusion on the visit, "Day 0". Accrual is planned for 20 months.

**Figure 1. C3731001 Study Design**

### 3. ENDPOINTS AND BASELINE VARIABLES: DEFINITIONS AND CONVENTIONS

This section describes the variable definitions and methods of derivation. Planned analyses and data presentations are described in [Section 6](#).

#### 3.1. Primary Endpoints

##### 3.1.1. Incidence of Adverse Events and Serious Adverse Events

For Years 1 to 3, all serious and non-serious AEs will be collected. For Years 4 and 5, all SAEs (regardless of relation to study intervention) and non-serious AEs determined to be related to study intervention by the investigator or where causality is unknown will be collected.

Incidence of AEs and SAEs, include clinically significant changes from pre vector dosing in:

- physical examinations;
- clinical laboratory assessments;
- immune parameters;
- vital signs;
- ECG;
- liver imaging.

Abnormal findings that meet the criteria for AE reporting in this study are to be reported as AEs, and thus will be included in the primary endpoint summary table.

### 3.1.2. Factor VIII Activity

All samples collected from participants for plasma factor FVIII activity levels will be analyzed by central and local laboratories. In the central laboratory, FVIII activity will be assessed both by chromogenic and one-stage clotting assays. In local laboratories, FVIII activity will be assessed by chromogenic or one-stage clotting assay based on local laboratory's usual practice. Only central laboratory results will be used for analysis. Raw values reported as below the limit of quantification (BLoQ) will be converted to a numeric value for analyses (summaries and plots). The numeric value of 0.009 international units (IU)/ milliliter (mL), or 0.9 % normal, will be assigned prior to analysis for both one-stage clotting assay and chromogenic assay when the originally reported results were <0.010 IU/mL and <0.030 IU/mL, respectively. Summary tables and plots will use "% normal" as units, where % normal = IU/ mL x 100.

FVIII activity assessments assigned to a protocol-defined visit, will be analyzed for that visit. If FVIII activity is assessed as an unscheduled visit, the assessment date will be converted to a day relative to the investigational product (IP) infusion and divided by 7. The integer value of the quotient will be the 'week' assigned to the unscheduled assessment. If the derived week for an unscheduled assessment falls within the visit window of a protocol-defined visit, the unscheduled assessment result will be included in summaries and analyses for the mapped protocol-defined visit. Additional windowing details for mapping weeks to visits can be found in the Analysis and Reporting plan.

Per protocol, if a participant has FVIII replacement therapy around the day of a visit when FVIII activity measurement is scheduled, sample collection should be postponed at least 48 or 72 hours based on the FVIII product used (standard half-life or extended half-life respectively). For all FVIII activity summaries and analyses (including plots), any FVIII activity values measured within 96 hours after administering exogenous FVIII replacement therapy will be excluded as ineligible. In addition, FVIII activity assessments collected after a participant initiates or resumes a prophylaxis regimen will be excluded. If there are multiple observations for an individual in the same time window, for all FVIII activity analyses with the exception of geometric mean analyses, the average of an individual's FVIII activity values within the same time window will be used.

A listing of individual FVIII activity values for each participant will show assay used, observed values in collected units and in % normal units, visit name (including unscheduled visits), and the analysis visit (the visit to which the value has been slotted, either from the visit name, or derived by taking the integer part of relative day/7). Measurements within 96 hours after a FVIII replacement infusion or after a participant initiates or resumes a prophylaxis regimen, will be flagged in the listing and excluded from plots.

Group-level plots will be limited to protocol-defined study visits. If the derived week for an unscheduled assessment falls within the visit window of a protocol-defined visit, the unscheduled value will be displayed. Individual-level plots will use unslotted unscheduled

visit data points. Baseline for FVIII activity is defined as the latest valid measurement prior to IP infusion.

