1.3. Schedule of Activities (SoA)

Table 1 provides an overview of the protocol visits and procedures. Refer to the [Study Assessments and Procedures](#) section of the protocol for detailed information on each procedure and assessment required for compliance with the protocol. The investigator may schedule visits (unplanned visits) in addition to those listed in Table 1, in order to conduct evaluations or assessments required to protect the well-being of the participant.

Table 1. Schedule of Activities

Procedure	Screening	Baseline ^a	Infusion Center		Day 7 (±1 day)	Weeks 2, 4, 6, 8, 10, 12 (±3 days)	Weeks 16, 20, 24, 28, 32, 36, 40, 44, 48, 52 (±1 wk)	Months 24, 36, 48, 60 (±1 M)	Early Termination Visit
			Day 0 ^b	Day 1					
Informed consent	X								
Neutralizing activity to AAV2/6	X ^c								
Medical history, inclusion/exclusion criteria	X								
Chest X-ray ^d	X								
Urinalysis with microscopic examination	X								
Liver elastography ^{d,e}	X								
Hepatitis B panel, HCV antibody, HCV RNA viral load, and HIV RNA viral load and HIV-1/2 antibody assay	X								
FVIII genome sequencing ^f	X								
Circulating alpha fetoprotein level ^g	X					X (wk 12 only)	X (wks 24 and 52)	X	X
Liver MRI ^{d,g}	X					X (wk 12 only)	X (wks 24 and 52)	X	X
12-lead ECG ^d	X						X (wk 52)	X	
Physical examination including vital signs, height, and weight ^h	X	X (weight only)			X	X (wks 4, 8, 12)	X (wks 20, 28, 36, 44, 52)	X	X

Table 1. Schedule of Activities

Procedure	Screening	Baseline ^a	Infusion Center		Day 7 (±1 day)	Weeks 2, 4, 6, 8, 10, 12 (±3 days)	Weeks 16, 20, 24, 28, 32, 36, 40, 44, 48, 52 (±1 wk)	Months 24, 36, 48, 60 (±1 M)	Early Termination Visit
			Day 0 ^b	Day 1					
Vital Signs ^q when not already included with physical examination			X	X					
Concomitant medication review	X	X	X	X	X	X	X	X ^t	X
CBC with differential and platelet count	X	X	X	X		X (wks 4, 8, 12)	X (wks 28, 52)	X	X
Serum chemistry	X	X	X	X		X	X	X	X
Liver panel ⁱ	X	X			X (2x in first wk)	X (2x/wk)	X ^j (2x/wk, wks 13-20)	X (every 6m from Wk52 to Mth60)	X
Coagulation screen (PT, INR, and aPTT)	X	X	X			X (wks 4, 8, 12)	X	X	X
Anti-AAV antibodies to AAV2/6 (total and neutralizing)		X				X (wk 4 only)	X (wk 52 only)	X	
FVIII activity ^{k,m}	X	X		X	X	X (1x/wk)	X (1x/wk through Wk 20) ^l	X (every 6m from Wk52 to Mth60)	X
FVIII antigen ^v	X	X		X	X	X (1x/wk)	X ^l	X	X
FVIII inhibitor titer ⁿ	X	X		X		X ^l (wks 4, 8, 12)	X ^l	X (every 6m from Wk52 to Mth60)	X

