## 5. GENERAL METHODOLOGY AND CONVENTIONS

All statistical analyses will be performed using SAS system version 9.4 or higher.

All summary statistics will be reported stratifying by cohort/dose level (planned or received, depending on the study population) and overall. Relative day 1 is defined as the date of visit “Day 0”, the start of the IP infusion.

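### Truncating relative day/7 labels unscheduled FVIII samples one week early on 2 of the 7 in-window days at the Week 2 to 12 visits

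*SAP*

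**What the plan says.** SAP 3.1.2 keeps any FVIII assessment that already carries a protocol visit at that visit. For an unscheduled assessment it derives a week from the relative day divided by 7: "The integer value of the quotient will be the" week. The listing description in the same section repeats the rule, with the analysis visit "derived by taking the integer part of relative day/7". Day numbering comes from SAP 5: "Relative day 1 is defined as the date of visit" Day 0, which is the infusion date.

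If the derived week lies within a protocol visit's window, "the unscheduled assessment result will be included in summaries and analyses for the mapped protocol-defined visit". Where a participant has several values in a window, "the average of an individual's FVIII activity values within the same time window will be used", except in the geometric mean analyses. Further detail on mapping weeks to visits is left to the Analysis and Reporting plan.

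The schedule of activities (Protocol 1.3) gives "Weeks 2, 4, 6, 8, 10, 12 (±3 days" and "Weeks 16, 20, 24, 28, 32, 36, 40, 44, 48, 52 (±1 wk" as the visit windows, and Day 7 has ±1 day. FVIII activity is sampled weekly into this period: "X (1x/wk through Wk 20".

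**The concern.** A bin formed by truncation starts near the nominal day and runs forward. A visit window of ±3 days is centred on the nominal day. The two cannot coincide, so an unscheduled sample drawn early in a window is labelled with the week before, and a sample drawn after the window closes is labelled with the visit just past.

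The time course of FVIII activity is a primary objective, and Weeks 2 to 8 precede Week 9, which SAP 6.1.2.1 names as the start of steady state. The by-visit values also feed the Cohort 4 box plots that help to judge when steady state begins (SAP 6.3.5). If expression is rising, averaging a later sample into an earlier visit raises that visit's value. An in-window sample labelled with an odd week may drop out of its own visit's summary, because between Weeks 2 and 12 the schedule names only even-week visits.

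**Working it through.** The documents state no figure to reproduce, so the check lists every in-window day.

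**Inputs.** Let d be the post-infusion day, with infusion on Day 0. The SAP's relative day is then r = d + 1 (SAP 5). The derived week is floor(r/7) (SAP 3.1.2). The window for k = 2, 4, 6, 8, 10, 12 is d = 7k-3 to 7k+3 (Protocol 1.3).

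**Step 1: the bin that the rule creates.** floor((d+1)/7) = k holds when 7k ≤ d+1 ≤ 7k+6, so d = 7k-1 to 7k+5. The bin's centre is 7k+2, which is 2 days later than the window's centre of 7k.

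**Step 2: compare bin and window.**

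| Visit | Schedule window (d) | Truncated bin (d) | In-window days labelled a week early | Out-of-window days given this label |
|---|---|---|---|---|
| Week 2 | 11-17 | 13-19 | 11, 12 | 18, 19 |
| Week 4 | 25-31 | 27-33 | 25, 26 | 32, 33 |
| Week 6 | 39-45 | 41-47 | 39, 40 | 46, 47 |
| Week 8 | 53-59 | 55-61 | 53, 54 | 60, 61 |
| Week 10 | 67-73 | 69-75 | 67, 68 | 74, 75 |
| Week 12 | 81-87 | 83-89 | 81, 82 | 88, 89 |

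For example, day 25 has r = 26, and 26/7 = 3.71 truncates to Week 3. Day 33 has r = 34, and 34/7 = 4.86 truncates to Week 4, although day 33 is 5 days after nominal Week 4 and 2 days before nominal Week 5.

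The total is 12 of 42 in-window days, or 2 of 7 at each visit, always one week early. If relative day meant elapsed days (infusion = 0), it would be 3 of 7.

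**Step 3: other visits.** At Day 7 (±1 day), days 6 to 8 all give Week 1, so 0 of 3 are misplaced. At Weeks 16 to 52 (±1 week), 0 of 15 in-window days fall outside weeks k-1 to k+1. Testing the integer week against that range would, however, admit offsets from -8 to +12 days.

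**Step 4: size.** The documents give no rise curve, so a linear rise to plateau over T days is assumed. The 63-day case ends at Week 9; 35 and 84 days are assumed bounds. The shift as a share of plateau is (days late)/T, and averaging with one scheduled value taken on the nominal day halves it.

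| T (days) | 2-day bin shift | After averaging | Sample 4-5 days late | After averaging |
|---|---|---|---|---|
| 35 | 5.7% | 2.9% | 11.4-14.3% | 5.7-7.1% |
| 63 | 3.2% | 1.6% | 6.3-7.9% | 3.2-4.0% |
| 84 | 2.4% | 1.2% | 4.8-6.0% | 2.4-3.0% |

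**Step 5: test of rounding as a remedy.** Rounding (r-1)/7 to the nearest integer misplaces 0 of 42 days at Weeks 2 to 12. It does not reproduce the other windows: Week 1 becomes days 4-10 against 6-8 in the schedule, and accepting weeks k-1 to k+1 at Weeks 16 to 52 admits offsets of -10 to +10 days against ±7.

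**The case against.** The best defence is that the rule reaches few samples and few outputs. A sample with a visit name keeps its visit however early in the window it was drawn. The documents do not say how many samples are unscheduled, or whether the odd-week weekly draws carry visit names of their own. Individual plots use actual times. The yearly Cohort 4 geometric means take all eligible values from steady state onward, unscheduled ones included, without averaging by visit. All analyses are descriptive (SAP 5.1), SAP 3.3.5 acknowledges high variability between participants, and a 2-day shift is smaller than the ±3 days that the schedule tolerates. All of this stands, and it limits the point to a small one.

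The deferral to the Analysis and Reporting plan stands in part. That plan may decide whether a sample labelled week k finally enters visit k, so the effect on the summaries cannot be fully determined from these documents. But only the step from week to visit is deferred. The step from day to week is fixed in the SAP, and a different rule elsewhere would contradict it.

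A reader might infer three stronger things, none of which the documents support:

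- That 29% of FVIII samples are misassigned. The 2 of 7 counts calendar days in a ±3-day window, and applies only to unscheduled samples.
- That the primary endpoint is biased upward. The geometric means are touched only at boundaries, and the direction elsewhere depends on FVIII rising. Weekly sampling also continues when a participant is on steroids or develops an inhibitor (Protocol 1.3, footnote l), when a rise cannot be presumed.
- That valid data are discarded. The listing keeps every value; any loss is from by-visit tables and group plots.

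**Conclusion.** The mismatch is real and exact on the documents' own definitions, and it is minor in effect. For unscheduled FVIII samples around Weeks 2, 4, 6, 8, 10 and 12, the rule labels 2 of 7 in-window days one week early and gives week k's label to days 7k+4 and 7k+5, which lie outside its window. The by-visit summaries, group plots and Cohort 4 steady-state box plots are the outputs at risk.

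The count rests only on the SAP's day numbering and the schedule windows. The size of about 2% to 6% of plateau for a 2-day shift, or about 1% to 3% after averaging with one scheduled value, rests on an assumed linear rise over 35 to 84 days. How often it occurs depends on the number of unscheduled samples, which the documents do not give.

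**What to change.** In both places in SAP 3.1.2, drop the truncation and assign an unscheduled sample by its post-infusion day (relative day - 1), matched directly to the schedule windows: Day 7 ±1 day; Weeks 2 to 12 ±3 days; Weeks 16 to 52 ±7 days; Months 24 to 60 ±1 month, which SAP 3.1.2.1 already takes as 4 weeks. Where the listing needs a week label, use (relative day - 1)/7 rounded to the nearest integer. Whole days cannot produce a tie.

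The same edit should say whether the odd-week weekly draws count as analysis visits. If they do not, direct matching leaves those between Weeks 2 and 12 outside every window, and this should be a stated choice. The Analysis and Reporting plan should be checked against the new text.

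The cost is a few lines of SAP text and code. No visit, procedure or data collection changes.

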Table 1. Schedule of Activities

Procedure	Screening	Baseline ^a	Infusion Center		Day 7 (±1 day)	Weeks 2, 4, 6, 8, 10, 12 (±3 days)	Weeks 16, 20, 24, 28, 32, 36, 40, 44, 48, 52 (±1 wk)	Months 24, 36, 48, 60 (±1 M)	Early Termination Visit
			Day 0 ^b	Day 1					

- i. Both local and central LFTs will be performed. At Screening, liver panel will be performed twice, at least 1 week apart. Following infusion, LFTs will be done twice a week from the first collection approximately 3 to 4 days after Day 0 and continuing until Week 20. The local laboratory results may be utilized for the investigator to react promptly if an ALT elevation occurs. Note: Local and central LFTs are drawn tandemly twice weekly.
- j. Continue central and local LFT assessments twice per week if participant is receiving steroids. LFT assessments will continue twice weekly until 3 consecutive results demonstrate stable liver function. At this time LFT assessment may be decreased to once a week.
- k. If a participant has FVIII administration around the day of a visit when FVIII activity is scheduled, sample collection should be postponed at least 48 or 72 hours based on the FVIII product used (short half-life or long half-life, respectively).
- l. If a participant is receiving steroids or if a participant develops an inhibitor, weekly assessments of FVIII activity, FVIII antigen and FVIII inhibitor titer will continue.
- m. Central and local FVIII activity assessment will be performed. After Week 52, measurement of FVIII activity will be done every 6 months, and may increase if warranted by changes in FVIII activity or presence of inhibitor. Mobile phlebotomy can be used as needed.
- n. Central FVIII inhibitor titer assessment will be conducted. After Week 52, measurement of FVIII inhibitor titer may increase if warranted by changes in FVIII activity or the presence of inhibitor.
- o. Vector genomes in plasma, saliva, urine, stool, and semen by PCR (unless three previous consecutive specimens have been negative, see footnote p). On Day 0, vector genome titer should be obtained in **plasma only** at 12 hours from the start of the infusion ± 1 hour.
- p. Collection will only continue until three consecutive negative samples are obtained on a sample-type basis and every 1 month after Week 52 to Month 60 [±1 month]). For example, after urine sample results are negative 3 consecutive times, the urine sample will stop being collected while the other samples may continue if they are positive.

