6.5. Concomitant Therapy

All concomitant medications and therapy taken through Month 36 must be captured in the CRF. After Month 36, only concomitant medications and therapy associated with SAEs, AEs related to the study drug, or to AEs with an unknown cause will be reported through Month 60 or the ETV, if applicable. See Section [8.3.1](#) for AE reporting requirements.

The investigator will record all concomitant medications including those given in treatment of AEs on the concomitant medication page in the participant's CRF. Any medication taken by the participant from 30 days prior to screening throughout the course of the study, including over-the-counter medicinal products, dietary supplements, and herbal medications, should be recorded on this form. A short course of prednisone may be instituted either as prophylaxis or post AAV exposure if an immune reaction to the AAV capsid develops (Section [10.7](#)). Any treatment with prednisone and pre-treatment with acetaminophen and diphenhydramine hydrochloride should be recorded on the concomitant medications page.

Participants enrolled in this study who previously received prophylactic FVIII replacement regimens will be required to switch to on-demand therapy approximately 2 weeks after infusion with SB-525 (PF-07055480), pending data shows it is safe to do so. The use and timing of FVIII replacement will be monitored closely in this study and will influence the timing of PD assessments for FVIII activity. There is no washout period per se, but all participants will be switched to an on-demand regimen approximately 2 weeks after infusion and subsequently modulate their FVIII replacement use according to their needs. All participants are to carefully record the date and time of each FVIII administration in an e-Diary, so that the elapsed time between their last FVIII administration and each FVIII level collection can be collected. For participants using short half-life replacement products, the resulting FVIII levels are valid only if elapsed time is more than 48 hours. For participants using extended half-life FVIII replacement products, this time is extended to 72 hours. Of note, 48 and 72 hours are reference values, these times can be modified depending on the participant profile (slow versus fast metabolizers) and the prescribing information of each product. The investigator may recommend a different time for his/her study participant after discussion with the medical monitor.

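### The protocol allows FVIII activity draws from 48 or 72 h after replacement, but the SAP discards values within 96 h; after Week 52 a lost draw is one of two planned that year

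*SAP*

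**What the plan says.** **Sampling rule (protocol).** Footnote k of the Schedule of Activities deals with FVIII given around a scheduled visit: "sample collection should be postponed at least 48 or 72 hours based on the FVIII product used (short half-life or long half-life, respectively". Section 8.1.1 repeats this. Section 6.5 sets the validity standard. For short half-life products, "the resulting FVIII levels are valid only if elapsed time is more than 48 hours", and for extended half-life products the time becomes 72 h. It adds that "48 and 72 hours are reference values, these times can be modified depending on the participant profile". On background treatment it says "There is no washout period per se, but all participants will be switched to an on-demand regimen approximately 2 weeks after infusion".

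**Analysis rule (SAP).** Section 3.1.2 restates the 48/72 h sampling rule and in its next sentence applies a longer one for all products: "any FVIII activity values measured within 96 hours after administering exogenous FVIII replacement therapy will be excluded as ineligible". Section 3.1.2.1 repeats 96 h for the yearly geometric means, which section 6.1.2.1 summarises for Cohort 4. Section 3.3.1 applies 96 h to FVIII antigen. Excluded activity values remain as flagged listing entries. Values after prophylaxis is initiated or resumed are removed by a separate rule.

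**Frequency.** Per footnote m, "After Week 52, measurement of FVIII activity will be done every 6 months", with more sampling if activity changes or an inhibitor appears, and "Mobile phlebotomy can be used as needed". The annual visits are headed "Months 24, 36, 48, 60 (±1 M" (plus or minus one month).

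**The concern.** Both rules are current text and they do not meet. A site that follows the protocol exactly can collect a sample that the SAP will not use. The postponement instruction makes this more likely, because a draw moved to the 48 or 72 h minimum lands inside the excluded period. The SAP version history shows that the cutoff was deliberately raised from 72 h, but the sampling text was not brought into line.

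The losses fall only on participants who recently infused FVIII. These are plausibly the participants with lower expression, so the missing values may be informative; that is inference, not something the documents show. The cost is greatest in Years 2–5, where planned sampling is sparse and where protocol section 9.4.3 says follow-up is meant to show durability. With no imputation, losing one of two draws leaves a yearly geometric mean resting on one value. Losing both removes the participant from that year's summary.

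The point is confined to draws after the switch to on-demand therapy.

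**Working it through.** The documents give no figure for this loss, so there is none to reproduce.

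**1. Excluded but protocol-compliant interval.** Standard half-life: 96 − 48 = 48 h. Extended half-life: 96 − 72 = 24 h.

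**2. Planned draws per analysis window** (Schedule of Activities; windows from SAP 3.1.2.1; Week 9 start from SAP 6.1.2.1).
- Year 1: weekly in Weeks 9–20 = 12, plus Weeks 24, 28, 32, 36, 40, 44, 48 and 52 = 8. The total is 20, and 1/20 = 5%.
- Years 2–5, one draw every 26 weeks: Weeks 78 and 104; 130 and 156; 182 and 208; 234 and 260. That is 2 per window and 8 in all, so one loss is 1/2 = 50% of the window.

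**3. Chance that a draw is lost.** Assume on-demand infusions follow a Poisson process at L per year. L is an assumption. The value 12 is borrowed from inclusion criterion 5, the pre-study minimum number of bleeds for on-demand participants, and is high for the period after treatment.
- A: the draw happens to fall 72–96 h after the last infusion: exp(−3L/365.25) − exp(−4L/365.25).
- B: the draw happens to fall 48–96 h after it: exp(−2L/365.25) − exp(−4L/365.25).
- C: every postponed draw is taken exactly at the minimum, so any infusion in the 96 h before the planned time costs the value: 1 − exp(−4L/365.25).

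With p the per-draw probability, the chance that a later-year window loses at least one of two draws is 1 − (1 − p)², treating the draws as independent. The expected loss over Years 2–5 is 8p. The last two columns run from A to C.

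| L per year | A | B | C | At least 1 of 2 lost | Expected lost of 8 |
|---|---|---|---|---|---|
| 1 | 0.27% | 0.54% | 1.09% | 0.5–2.2% | 0.02–0.09 |
| 5 | 1.30% | 2.63% | 5.33% | 2.6–10.4% | 0.1–0.4 |
| 12 | 2.93% | 5.96% | 12.31% | 5.8–23.1% | 0.2–1.0 |

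Several infusions clustered within one bleed would lower these figures.

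**4. Is 96 h reasonable as an analysis rule?** Protocol 2.2.1 gives a 12 h half-life for standard FVIII and about 1.5-fold for longer-acting products, so 1.5 × 12 = 18 h. The share of the infused rise still present is 0.5^(t/half-life).
- At the protocol minimum: 0.5^(48/12) = 0.5^(72/18) = 6.25%.
- At 96 h: 0.5^(96/12) = 0.4% (standard); 0.5^(96/18) = 2.5% (extended).

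The longer cutoff clearly reduces carry-over. The defect is the lack of alignment, not the 96 h.

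**The case against.** The strongest reply is that nothing contradicts. The protocol times are minimums, section 6.5 lets the investigator agree a different wait with the medical monitor, and protocol section 9 allows the SAP to modify what the protocol outlines. A stricter analysis filter on top of a collection minimum is coherent, and removing values from recently infused participants is its purpose. Several features soften the effect:
- Unscheduled values enter the geometric mean, and all available data are used.
- Sampling rises to at least every 3 months when activity exceeds 150%.
- Excluded values remain visible in the listing.
- The analyses are purely descriptive.

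The infusion rates are assumed, and the ends of each range describe different site behaviour. Laboratory instructions and the Analysis and Reporting plan, which are not available here, might already ask for 96 h.

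Much of this stands. Loss is possible, not certain, and two draws a year is the base schedule only. The one-month window is stated for the annual visits and not separately for the draws between them, although SAP 3.1.2.1 refers to one month of flexibility in the visit schedule after the first year.

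The central point survives. Permission to wait longer is not an instruction to do so, and authority to change the analysis does not tell sites when to draw. A flagged listing entry does not restore a yearly summary value.

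**Conclusion.** The concern holds. Protocol-compliant draws at 48–96 h (standard half-life) or 72–96 h (extended half-life) are excluded from all FVIII activity summaries, analyses and plots. In Year 1 one such loss is small. In Years 2–5 it removes half of the planned data in a participant's yearly window, unless extra draws are made. At an assumed 5–12 infusions a year, a later-year window loses at least one planned draw with probability 2.6–23%; at 1 a year this is 0.5–2.2%. These figures rest on randomly timed infusions, and the upper ends also assume that every postponed draw is taken at the protocol minimum with no redraw.

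The remedy is worth making because it is cheap and protects sparse long-term data. No inference depends on it, and the 96 h cutoff need not change.

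**What to change.** 1. **Reconcile the sampling and analysis passages** for visits after the switch to on-demand therapy. Where the visit window allows, chiefly after Week 52, ask sites to time the draw so that it meets the SAP cutoff, or to add a repeat draw that does. Leave Screening, Baseline, Day 7 and any draw taken during continuing prophylaxis as they are. Do not delay samples needed for safety monitoring (protocol 10.7) or dose decisions (4.1.2.1), and do not alter any treatment.
2. **Keep 96 h as the primary analysis rule and count its effect.** Report samples excluded by participant and year, separately for the 96 h rule and the prophylaxis rule. Optionally, add a sensitivity summary at the protocol's 48/72 h reference times, with a footnote that up to 6.25% of the infused rise may remain on the protocol's half-lives.
3. **Minor:** say which rule *valid* refers to in the SAP 3.1.2 baseline definition. At about three infusions a week (protocol 2.2.1) the mean gap is 168/3 = 56 h, so a pre-infusion sample can meet 48 h but not 96 h.

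The cost is a protocol clarification, one count table and, if wanted, one sensitivity table. Some draws move by one day (72 to 96 h) or two days (48 to 96 h), or a repeat is added; mobile phlebotomy is already allowed. At Weeks 2–12 (±3 days), and for weekly draws between visits with no stated window, the wait may not fit, so only the exclusion counts are asked for there.
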